Screening Criteria	1. Athletes and patients with traumatic brain injury 1) Age ≥ 18 and ≤ 80 years old with independent behavior ability or authorized legal representative. 2) Have a clear history of repetitive mild TBI, concussion or subconcussion. 3) The most recent head injury occurred 3 months ago. 2. Healthy Volunteers 1) Age ≥ 18 and ≤ 80 years old with independent behavior ability. 2) No history of repetitive mild TBI, concussion or subconcussion.

	3) Fully understands the nature of the study, and voluntarily participates and signs the informed consent.
Inclusion Criteria	On the basis of meeting the screening criteria, the participants need to fully understand the nature of the study, and sign the informed consent form.
Exclusion Criteria	
1. Athletes and patients with traumatic brain injury
 
1) Pregnant or lactating women.
 
2) History of other neurological diseases.
 
3) History of tumors, hematological diseases, severe cardiopulmonary diseases, hepatic failure or renal failure.
 
4) Have participated in clinical trials in the past four weeks.
 
5) The investigator believes that not appropriate for inclusion.
 
2. Healthy Volunteers
 
1) Pregnant or lactating women.
 
2) History of TBI or other neurological diseases.
 
3) History of tumors, hematological diseases, severe cardiopulmonary diseases, hepatic failure or renal failure.
 
4) Have participated in clinical trials in the past four weeks.
 
5) The investigator believe that not appropriate for inclusion.

Outcome Measures	
1. Blood tests (30-ml venous blood) for the following items.
 
1) Transcriptomics and proteomics high-throughput detection and quantitative verification;
 
2) Exosomal transcriptomics and proteomics high-throughput detection and quantitative verification;
 
3) Quantitative detection for classical biomarkers of traumatic brain injury, including S100B, GFAP, UCH-L1, NFL, T-Tau and p-Tau181.
 
2. Cognitive function tests, including RPQ, MMSE and MoCA.
 
3. Possible head MRI (plain scan and DTI sequence) examination and head PET (FDG-PET, Tau-PET and Amyloid-PET) examination

Reference standard	Clinical Approach to the Diagnosis of TES (Reams N., JAMA Neurology, 2016)

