3.1 Athletes and Patients with TBI

Screening Criteria

- 1) Age ≥ 18 and ≤ 80 years old with independent behavior ability or authorized legal representative.
- 2) Have a clear history of repetitive mild TBI, concussion or subconcussion.
- 3) The most recent head injury occurred 3 months ago.

Inclusion Criteria

On the basis of meeting the screening criteria, the participants need to fully understand the nature of the study, and voluntarily participate in the study and sign the informed consent form.

Exclusion Criteria

- 1) Pregnant or lactating women.
- 2) History of other neurological diseases.
- 3) History of tumors, hematological diseases, severe cardiopulmonary diseases, hepatic failure or renal failure.
- 4) Have participated in clinical trials in the past four weeks.
- 5) The investigator believe that not appropriate for inclusion.

Withdrawal criteria

The subject is considered as withdrawal if he/she could not complete the trial for following reasons:

- 1) The subject decides to withdraw from the study.
- 2) Lost to follow-up.
- 3) The doctor or the researcher asks the subject to withdraw from the study (e.g. poor compliance).

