3.2 Healthy Volunteers

Screening Criteria

- 1) Age \geq 18 and \leq 80 years old with independent behavior ability.
- 2) No history of repetitive mild TBI, concussion or subconcussion.
- 3) Fully understands the nature of the study, and voluntarily participates and signs the informed consent.

Inclusion Criteria

On the basis of meeting the screening criteria, the healthy volunteers need to fully understand the nature of the study, and sign the informed consent form.

Exclusion Criteria

- 1) Pregnant or lactating women.
- 2) History of TBI or other neurological diseases.
- 3) History of tumors, hematological diseases, severe cardiopulmonary diseases, hepatic failure or renal failure.
- 4) Have participated in clinical trials in the past four weeks.
- 5) The investigator believes that not appropriate for inclusion.

Withdrawal criteria

The subject is considered as withdrawal if he/she could not complete the trial for following reasons:

- 1) The subject decides to withdraw from the study.
- 2) Lost to follow-up.
- 3) The doctor or the researcher asks the subject to withdraw from the study (e.g. poor compliance).

4. Study procedure

Researchers initiate the study according to enrolled order after verification of the inclusion/exclusion criteria and collection of the informed consent.

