4.1 Screening assessment

Researchers should clearly evaluate each inclusion and exclusion criteria for the subjects. The following works need to be done during screening:

- 1) Filling general information, such as date of birth, gender, occupation, et al.
- 2) Medical history collection: History of head injuries (number, degree, time, et al.), past medical history, et al.
- 3) Basic physical examination.

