7.2 Informed consent and data protection agreement

It is the responsibility of the researchers to explain the objectives, study procedures, benefits and potential risks of the trial for each subject. The researchers should also receive the informed

consent in written form signed by the subject before starting the trial. For the subject who can not sign the informed consent for any reason, the informed consent form should be signed by their parents, legal guardians or protectors. The subject should also permit researchers and health survey organizations to check his or her original data in the trial. Thus, the reliability of the research findings could be ensured.

The information of each subject, such as address and telephone number, should be collected in detail. And the researcher/doctor should give the subject his or her phone number, so that the patient can contact with him or her when needed. This is also helpful for the research and medical care.

The informed consent form with the signature and the date should be kept properly by the researchers.

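### Does the rule that participants must understand and sign shut out those the protocol admits through a legal representative?

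*Protocol*

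**What the plan says.** Four places in the Protocol bear on the point.

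- **Screening, athletes and TBI patients (Section 3.1; same wording in the Protocol Abstract).** Criterion 1 reads "Age ≥ 18 and ≤ 80 years old with independent behavior ability or authorized legal representative".
- **Inclusion, same groups.** This applies in addition to screening. Section 3.1 says that "the participants need to fully understand the nature of the study, and voluntarily participate in the study and sign the informed consent form". The Abstract has a shorter form without the reference to voluntary participation: "the participants need to fully understand the nature of the study, and sign the informed consent form".
- **Consent (Section 7.2).** The default is written consent signed by the subject before the study starts. For a subject who "can not sign the informed consent for any reason, the informed consent form should be signed by their parents, legal guardians or protectors", others sign. This exception is not limited to any one group.
- **Healthy volunteers (Section 3.2).** Criterion 1 asks for age up to "80 years old with independent behavior ability" and names no representative.

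On procedure, Section 4 says "Researchers initiate the study according to enrolled order after verification of the inclusion/exclusion criteria and collection of the informed consent", and Section 4.1 says "Researchers should clearly evaluate each inclusion and exclusion criteria for the subjects". Section 4.2 then lists signing the consent form as the first item for included subjects.

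**The concern.** Screening and inclusion are cumulative. If a person passes screening only because a representative exists, and inclusion then requires that same person to understand the study fully and sign, the representative option appears to lead nowhere. The option also looks intended, since it is offered to the exposed groups and left out of the healthy volunteers' criterion.

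Section 7.2 does not obviously close the gap, because its words concern the signature. They do not say that understanding or voluntary agreement passes to someone else. With each criterion to be evaluated separately, a researcher might find no wording under which a represented candidate meets the inclusion criterion, even with a properly signed form in hand.

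At stake would be who may be enrolled in the two exposed groups. Section 1 of the Protocol describes cognitive decline across executive, visuospatial, memory and language domains, so reduced capacity is foreseeable. Two researchers could decide differently on the same candidate, or a represented participant could later be listed as failing an inclusion criterion.

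**Working it through.** The point is textual; no power, error rate or effect size enters. The check is whether one reading gives effect to every sentence, and whether the alternative is at least as natural.

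**Reading A: the inclusion criterion is absolute.** Only people who personally understand and sign may enter.
- The representative alternative in criterion 1 then admits nobody who could not have entered without it, so half of that criterion is empty.
- The exception in Section 7.2 is also overridden wherever the reason for not signing is incapacity, although its trigger is not limited to particular reasons.
- Two provisions lose force so that one sentence can be taken literally.

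**Reading B: the inclusion criterion states the default, and Section 7.2 states the exception.**
- Criterion 1 keeps its meaning: a person with a representative can be considered.
- Section 7.2 keeps its meaning: where the subject cannot sign, another person does.
- The inclusion criterion keeps its meaning for everyone able to consent.
- Section 7.2 itself places the default (the subject signs) directly beside the exception (others sign). A sentence elsewhere that repeats only the default does not thereby abolish the exception.

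Reading B loses nothing. Reading A loses two clauses, so B is the natural construction.

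**Are eligibility and consent separate gates?** The Section 4 sentence names verification of criteria and collection of consent as two things. But signing the form is itself part of the inclusion criterion in Section 3.1, and it appears again under Section 4.2. The protocol does not treat them as independent, so that sentence cannot show that a valid Section 7.2 consent fails inclusion.

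**Do the healthy volunteers show a different rule?** Only in part. Their criterion 1 has no representative option, but Section 7.2 covers every subject. The contrast supports the view that the option in Section 3.1 is meant to work, which again favours Reading B.

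**Do the signatory names conflict?** Criterion 1 speaks of an authorized legal representative; Section 7.2 lists parents, legal guardians or protectors. Legal guardians fall readily under the first term. Parents and protectors of adults fit less neatly, since everyone is at least 18. That is uneven terminology in general consent language, not two opposed rules.

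**Size.** The groups to which the representative option applies are:
- Abstract: 50 + 50 = 100 of 120, and 100/120 = 83.3%.
- Section 2.2: 30 + 30 = 60 of 70, and 60/70 = 85.7%.

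One person is 1/100 = 1.0% or 1/60 = 1.7% of the exposed participants. None of these is the number affected. That would be the exposed total multiplied by the share needing a representative, and the protocol gives no such share. Recruitment is by invitation to volunteer, and nothing says that any represented person is expected.

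**The case for a change.** The best case for amending is that Section 7.2 transfers a signature and nothing more. The inclusion criterion asks for three things: understanding, voluntary participation and a signature. Two of the three have no stated substitute. Eligibility and consent wording belongs in the protocol, so the gap cannot be left to an analysis plan. One clause and one consistent term for the signatory would close it at the cost of a short ethics submission.

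Much of this is accurate. No sentence says that the representative understands and agrees on the participant's behalf, and the two labels for the signatory do differ. That part stands as a drafting imperfection.

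It does not carry the further step to a contradiction. A contradiction needs two rules that cannot both be followed, and here they can. Provision for someone else to sign for a person who cannot would have little purpose if that person still had to show full understanding unaided; the practical reading is that the person who signs is the one who is informed and agrees. Nor is there an analytic consequence to set against the cost. The primary outcomes in Section 5.1 are blood levels of protein and RNA markers, and nothing in the protocol makes their measurement depend on who signed. The protocol also does not equate needing a representative with severe disease, so a shift in the severity mix of the exposed groups would be conjecture.

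Removing the representative option altogether would change a population rule to cure a wording gap. The text gives no support for that, as criterion 1 and Section 7.2 both point towards admission.

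**Conclusion.** The concern does not call for a change to the plan. The inclusion criterion is written in its default form, the exception sits in the section devoted to consent, and investigators who read the two together reach a coherent rule that also gives effect to screening criterion 1. What is left is an incomplete proxy clause and two names for the signatory: an ambiguity that users of the protocol would fill sensibly.

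No number of affected participants can be derived, and no effect on any marker estimate is shown. The 83.3% and 85.7% describe how large the exposed groups are, not how many eligibility decisions are in doubt.

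This rests on two assumptions: that Section 7.2 is read as a general exception covering incapacity, as its open-ended trigger suggests; and that the person who signs under it is the one informed about the study. If the study team had meant the inclusion criterion to be absolute, the representative wording in Section 3.1 would serve no purpose, and nothing in the Protocol indicates that intention.

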3.2 Healthy Volunteers

Screening Criteria

- 1) Age \geq 18 and \leq 80 years old with independent behavior ability.
- 2) No history of repetitive mild TBI, concussion or subconcussion.
- 3) Fully understands the nature of the study, and voluntarily participates and signs the informed consent.

Inclusion Criteria

On the basis of meeting the screening criteria, the healthy volunteers need to fully understand the nature of the study, and sign the informed consent form.

Exclusion Criteria

- 1) Pregnant or lactating women.
- 2) History of TBI or other neurological diseases.
- 3) History of tumors, hematological diseases, severe cardiopulmonary diseases, hepatic failure or renal failure.
- 4) Have participated in clinical trials in the past four weeks.
- 5) The investigator believes that not appropriate for inclusion.

Withdrawal criteria

The subject is considered as withdrawal if he/she could not complete the trial for following reasons:

- 1) The subject decides to withdraw from the study.
- 2) Lost to follow-up.
- 3) The doctor or the researcher asks the subject to withdraw from the study (e.g. poor compliance).

4. Study procedure

Researchers initiate the study according to enrolled order after verification of the inclusion/exclusion criteria and collection of the informed consent.

4.1 Screening assessment

Researchers should clearly evaluate each inclusion and exclusion criteria for the subjects. The following works need to be done during screening:

- 1) Filling general information, such as date of birth, gender, occupation, et al.
- 2) Medical history collection: History of head injuries (number, degree, time, et al.), past medical history, et al.
- 3) Basic physical examination.

4.2 Included subjects

- 1) Signing the informed consent form.
- 2) Blood test
 - Transcriptomics and proteomics high-throughput detection and quantitative verification;
 - Exosomal transcriptomics and proteomics high-throughput detection and quantitative verification;
 - Quantitative detection for classical biomarkers of traumatic brain injury, including S100B, GFAP, UCH-L1, NFL, T-Tau and p-Tau181.
- 3) Cognitive function tests, including RPQ, MMSE and MoCA.
- 4) Neuro-imaging examinations (if eligible): head MRI (plain scan and DTI sequence) and head PET (FDG-PET, Tau-PET and Amyloid-PET) examination

5. Evaluation Parameters

5.1 Primary outcome parameters

- 1) Blood level of novel protein biomarkers for CTE/TES screened out by multi-omics high-throughput detection, and further verified using ELISA assay.
- 2) Blood level of novel RNA biomarkers for CTE/TES screened out by multi-omics high-throughput detection, and further verified using RT-PCR.

5.2 Secondary outcome parameters

- 1) Blood level of classical biomarkers for CTE/TES, including S100B, GFAP, UCH-L1, NFL, T-Tau and p-Tau181 detected by ELISA assay.

2) Cognitive function tests, including RPQ, MMSE and MoCA.

3) Head MRI (plain scan and DTI sequence) examination using the Discovery MR750 3.0T system (GE Healthcare, Chicago, IL, USA)

4) PET examination using the Discovery 710 PET-CT system (GE Healthcare). The FDG PET ([¹⁸F]-FDG) scan, tau PET scan ([¹⁸F]-T807) and β -amyloid PET scan ([¹⁸F]-florbetapir) will be arranged on consecutive days.

6. Withdrawal of the subject

The subject has the right to withdraw from this trial at any time for any reasons. The researcher should have a thorough understanding on the reasons for withdrawal. Doctors and researchers also have the right to stop the subject from continuing to participate in the trial at any time during the research. In addition, subjects with early withdrawal should not be replaced by others.

As too many subjects withdrawing from the trial will lead to unreliable results, unnecessary withdrawal should be avoided. The falling rate of the trial should be controlled within 20%.

7. Trial Management

7.1 Ethics

To obtain the approval documents of the clinical trial, researchers should submit the trial protocol and a copy of the research documents including the informed consent form to the ethics committee.

The approval documents from the ethics committee should be accompanied by the name list of ethics committee members and their respective responsibilities. These documents will be delivered to the researchers in written form before the start of the study. In addition, a copy of the approval documents needs to be provided to the sponsor by the researchers.

Any safety-related issues must be promptly reported to the ethics committee, which includes revision on the trial protocol and modification on the subject information page. The end or early termination of the trial should also be reported.

7.2 Informed consent and data protection agreement

It is the responsibility of the researchers to explain the objectives, study procedures, benefits and potential risks of the trial for each subject. The researchers should also receive the informed

consent in written form signed by the subject before starting the trial. For the subject who can not sign the informed consent for any reason, the informed consent form should be signed by their parents, legal guardians or protectors. The subject should also permit researchers and health survey organizations to check his or her original data in the trial. Thus, the reliability of the research findings could be ensured.

The information of each subject, such as address and telephone number, should be collected in detail. And the researcher/doctor should give the subject his or her phone number, so that the patient can contact with him or her when needed. This is also helpful for the research and medical care.

The informed consent form with the signature and the date should be kept properly by the researchers.

7.3 Withdraw from the trial

The researchers have the right to ask the subject to withdraw from the clinical trial. But whenever the subject withdraws, the researcher should explain and record the reasons.

7.4 Subjects privacy

The researchers should protect the privacy of the subject. All documents submitted to the sponsor can only be identified using the subject's number instead of the name or admission number. In addition, the grouped table that records the correspondence between the subject's name and number can only be kept by the researcher, and could not be submitted to the sponsor

7.5 Modification of the trial protocol

The trial protocol is determined by researchers and the sponsor together, and approved by the ethics committee before starting the trial. During the research, any proposed modification on the trial protocol should be submitted to the principal investigator and the sponsor. The revised proposal will be then reviewed, and submitted to the ethics committee. The clinical research can only be resumed after the re-approval of the ethics committee.

7.6 Original records certification

Researchers should ensure that the subject's privacy is protected when collecting and organizing data. In addition, the data manager is authorized to review the original records in order to confirm the accuracy of the original data and to know the real-time progress of the trial.

7.7 Documents on file

According to relevant laws and regulations, researchers should keep the original records properly. All research duplicates should be retained for at least 5 years from the end of the study.

